10.1.2 Collection and Reporting

Every AE occurring during the clinical trial should be recorded on the corresponding page of the Case Report Form. Every AE should be documented, monitored and followed until the AE is recovered or until the safety follow-up visit is performed at 30 days after the withdrawal of the investigational product.

Clinically significant abnormal laboratory findings should be monitored regularly by specific analysis until their values return within the normal reference ranges, to the baseline value or until an adequate explication of the out of range value has been found. Per the applicable regulations, AEs are collected from the moment of signature of the informed consent form until up to 30 days after the withdrawal of the investigational product.

For every AE, the following parameters will be documented by the investigator:

- A clear description of the event using the adequate medical terms;
- The seriousness of the event;
- The severity or grade of the event (severity criteria are described in the next paragraph);
- The onset and end dates of the event;
- The actions taken and the necessity to introduce a corrective treatment or not;
- Whether the AE caused or not the withdrawal of the subject from the study;
- The outcome of the event. In case of a non-fatal outcome, the AE should be documented until recovered, until the return to baseline conditions of the event or

Protocole NEXT-REGIRI -Version 6.0 du 09/11/2023

Page **69** sur **86**

until stabilization of the event's sequelae (the nature of the sequelae should be documented);

- The causality between the event and the investigational product;
- The eventual causality between the event and the study procedures (time laps without treatment, complementary assessments required by the protocol, etc....), the study indication, a concomitant treatment, a concomitant pathology or another factor.

10.1.3 Severity Criteria

The severity criteria should not be mistaken with the seriousness criteria which determine the conditions of notification. The severity or grade of adverse events is evaluated by the investigator following the NCI-CTCAE classification version 5.0 (appendix 9).

The CTCAE displays Grades 1 through 5 with unique clinical descriptions of severity for each AE based on this general guideline:

- Grade 1 = Mild; asymptomatic or mild symptoms; clinical or diagnostic observations only; intervention not indicated.
- Grade 2 = Moderate; minimal, local or non-invasive intervention indicated; limiting age-appropriate instrumental ADL*.
- Grade 3 = Severe or medically significant but not immediately life-threatening; hospitalization or prolongation of hospitalization indicated; disabling; limiting self-care ADL**.
- Grade 4 = Life-threatening consequences; urgent intervention indicated.
- Grade 5 = Death related to AE.

*Instrumental ADL refer to preparing meals, shopping for groceries or clothes, using the telephone, managing money, etc.

**Self-care ADL refer to bathing, dressing and undressing, feeding self, using the toilet, taking medications, and not bedridden.

10.2 Serious Adverse Events, New Event and Urgent Safety Measure (USM)

10.2.1 Definition

A Serious Adverse Event (SAE) is an adverse event which:

- results in death
- is life-threatening
- requires in-patient hospitalization or prolongation of existing hospitalization,
- results in persistent or significant disability or incapacity
- Is a congenital anomaly or birth defect
- Is medically relevant

Life-threatening in this context refers to an event in which the patient was at risk of death at the time of the event; it does not refer to a reaction that hypothetically might have caused death if more severe.

A hospitalization scheduled by the protocol (biopsy, chemotherapy...) is not considered a SAE. A hospitalization or prolongation of hospitalization for technical, practical, or social reasons, in absence of an AE is not considered a SAE. A hospitalization planned prior to

patient enrollment is not considered a SAE, provided that his occurrence/outcome is clearly not aggravated by the investigational product.

The terms "disability" and "incapacity" match with all physical/psychological temporary or permanent handicaps, clinically significant with consequences for the physical or mental functioning and/or the quality of life of the patient.

Medical and scientific judgment should be exercised in deciding whether other situations should be considered serious events, such as important medical events that might not be immediately life-threatening or result in death or hospitalization but might jeopardize the patient or might require intervention to prevent one of the other outcomes listed above. Such events are considered serious with seriousness criterion "medically relevant". Examples of such events are allergic bronchospasm, torsade de pointes or convulsions.

Other examples of serious adverse events with seriousness criterion "medically relevant" are second primary malignancies and any suspected transmission via a medicinal product of an infectious agent.

For every SAE the investigator and the sponsor evaluate separately the possible causal relationship to the investigational product. These evaluations might be different one from the other (for example: in the investigator's opinion the SAE is not related to the investigational product and in the sponsor's opinion the SAE is related to the investigational product).

A New event (article R1123-46 du CSP) is:

Any new data leading to a reassessment of the benefits / risks balance of the research or product of the research, to changes in the use of the product or in the conduct on documents related to the research, or to discontinuation, arrest or modification of the research protocol or that of similar research.

For trials assessing first administration or use of a product in persons with no specific disease (healthy volunteer): any serious adverse event.

Urgent Safety Measure (USM) (articles L.1123-10 et R. 1123-62 CSP)

When a suspicion of an Unexpected Serious Adverse Reaction (SUSAR) or a New Event is likely to affect the safety of the subjects, or the IMP is likely to affect the safety of the participant who lend themselves to it with immediate endangerment, the sponsor and investigator put in place Urgent Safety Measure (USM) to protect the subjects against this immediate hazard, the sponsor and the investigator concerned take the necessary appropriate Urgent Safety Measures (USM).

10.2.2 Suspected Unexpected Serious Adverse Reaction

A SAE is qualified as a Suspected Unexpected Serious Adverse Reaction (SUSAR) when a causal relationship between the investigational product and the SAE is suspected and when the nature, the severity, the frequency or the evolution of the reaction does not match with the information available in the reference document. The sponsor evaluates the unexpectedness of the SAE by consulting:

- The SmPC for Regorafenib alone arm and for Irinotecan
- The latest version of the investigator's brochure (IB) for Regorafenib in the REGIRI arm.

10.2.3 Pregnancy

According to the regulatory recommendations with respect to potential genotoxicity and teratogenicity (CFTG 21/09/2020, version 1.1) the durations of contraceptives for women of childbearing potential (WOCBP) and men to ensure effective contraception during treatment with regorafenib are respectively 7 months and 4 months in men sexually active with women of childbearing potential after last dose of regorafenib.

For Irinotecan, the durations of contraceptives for women of childbearing potential (WOCBP) and men are respectively 6 months and 3 months in men sexually active with women .

For female patients treated with the investigational product, the treatment with this product should be discontinued immediately at the occurrence or suspicion of occurrence of pregnancy and the patient should be withdrawn from the study (after confirmation of the pregnancy by a urine or blood test).

The pregnancy should be followed up to determine outcome, including spontaneous or voluntary termination, details of the birth, and the presence or absence of any birth defects, congenital abnormalities, or maternal and/or newborn complications.

In accordance with the recommendations for fertility preservation, the investigator may propose to the patient a protocol of conservation of ovocytes for women and of sperm cells for men.

10.2.4 SAE, New Event, Urgent Safety Measure, and Pregnancy Notification Procedure

10.2.4.1 SAE Notification Procedure

Every SAE, expected or unexpected, occurring during the study period (from the moment of signature of the informed consent form until up to 30 days after the withdrawal of the investigational product) should be notified to the sponsor without any delay using the "Serious Adverse Event Notification Form" (Appendix 10). This form should be completed following the completion instructions (Appendix 10) and sent by email to the Clinical Research Pharmacovigilance Unit of the ICM.

Clinical Research Vigilance Unit
ICM – Institut régional de Cancérologie de Montpellier

[name]

[contact] - [contact]

Mail:

[contact]

For other safety information:

[contact]

Every SAE occurring beyond the 30 days period after the withdrawal of the investigational product, judged by the investigator to be related to the investigational product, should also be notified to the sponsor in the same conditions as every other SAE.

The "Serious Adverse Event Notification Form" should be completed in English and only one diagnosis or one symptom (except for linked symptoms) should be reported to enable MedDRA coding. If several symptoms are documented in the source documents, only the main symptom will be reported as verbatim on the notification form.

After the initial notification, a follow-up report should be completed and sent every time complementary information on the SAE becomes available. Finally, when the case is closed, a final report with the complete information should be completed and sent by email to the Clinical Research Vigilance Unit (E-Mail: [contact]).

Complementary information or clarification could be requested by the sponsor using Data Clarification Forms (DCFs). The sponsor could also ask the site to send the anonymized medical records or laboratory findings corresponding to the SAE. In case of a SUSAR a narrative of the case in English is to be provided by the investigator.

10.2.4.2 New Event / Urgent Safety Measure / Notification Procedure

Any New Event, and Urgent Safety Measure occurring during the study period should be notified to the sponsor without any delay to Clinical Research Pharmacovigilance Unit::

E-Mail: [contact]

Clinical Research Vigilance Unit

ICM – Institut régional de Cancérologie de Montpellier [name]

[contact]

10.2.4.3 Pregnancy Notification Procedure

Pregnancies and suspected pregnancies occurring during the study period (from the signature of the informed consent form until up to 2 months after the withdrawal of Regorafenib, and 3 months after the withdrawal of Irinotecan for female patients and for female partners of male patients are immediately reportable events. Every pregnancy or suspicion of pregnancy should be notified to the Sponsor without any further delay.

Pregnancy notification will be done using the "pregnancy notification form" (Appendix 11). This form should be completed using the filling instruction guide (Appendix 11) and sent by email to the pharmacovigilance unit (see above).

The Investigator should inform the Sponsor of the pregnancy follow-up by using the same "Pregnancy Notification Form" (Appendix 11) as for the initial notification. If the outcome of the pregnancy falls within the scope of the definition of serious adverse event (spontaneous abortion requiring hospitalization, fetal death, congenital abnormality...) the investigator should follow the Serious Adverse Event notification.

If it is a paternal exposure, the investigator must obtain the agreement of the pregnant women to collect the information on pregnancy.

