	 Progression during or within 3 months following the last administration of approved standard therapies, which must include a fluoropyrimidine (or raltitrexed), oxaliplatin, irinotecan, anti-VEGF therapy and an anti-EGFR therapy (for RAS wild-type tumors), encorafenib
	6. ECOG performance status ≤1
	7. Life expectancy of at least 3 months
	8. Patients with A/A CCND1 genotype of rs603965 CCND1
	9. Adequate bone marrow, liver and renal function as assessed by the following laboratory requirements conducted within 7 days of starting study treatment:
	➤ Lipase ≤ 1.5 x ULN
	➤ Total bilirubin ≤ 1.5 x ULN
	➤ Alanine aminotransferase (ALT) and aspartate aminotransferase (AST) ≤ 3.0 x ULN (≤ 5 x ULN for patients with liver involvement of their cancer)

- \triangleright Alkaline phosphatase (ALP) ≤ 2.5 x ULN (≤ 5.0 x ULN for patients with liver involvement for their cancer and/or have bone metastases)
- ➤ Platelet count ≥ 100,000/mm3; Hemoglobin (Hb) ≥ 9 g/dL; Absolute neutrophil count (ANC) ≥ 1,500/ mm3. Transfusion to meet the inclusion criterion
- ➤ Serum creatinine ≤ 1.5 x ULN
- 10. International normalized ratio (INR) ≤ 1.5 x ULN and partial thromboplastin time (PTT) or activated partial thromboplastin time (aPTT) ≤ 1.5 x ULN unless receiving treatment with therapeutic anticoagulation. Patients being treated with anticoagulant, e.g., heparin, will be allowed to participate provided no prior evidence of an underlying abnormality in these parameters exists. Close monitoring of at least weekly evaluations will be performed until INR and PTT are stable based on a pre-dose measurement as defined by the local standard of care
- 11. Women of childbearing potential must have a blood or urine pregnancy test performed a maximum of 7 days before start of study treatment, and a negative result must be documented before start of study treatment
- 12. Women of childbearing potential and men must agree to use adequate contraception before entering the study until at least respectively 7 months and 4 months after the last study drug administration of Regorafenib and respectively 6 months and 3 months after the last study drug administration of Irinotecan. The investigator or a designated associate is requested to advise the patient on how to achieve an adequate birth control. Adequate contraception is defined in the study as any medically recommended method (or combination of methods) as per standard of care.

Exclusion criteria

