- 12. Women of childbearing potential and men must agree to use adequate contraception before entering the study until at least respectively 7 months and 4 months after the last study drug administration of Regorafenib and respectively 6 months and 3 months after the last study drug administration of Irinotecan. The investigator or a designated associate is requested to advise the patient on how to achieve an adequate birth control. Adequate contraception is defined in the study as any medically recommended method (or combination of methods) as per standard of care.

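### The pregnancy notification window in section 10.2.4.3 is shorter than the protocol's own contraception period in three of four drug-by-sex combinations

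*Combined protocol and SAP*

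**What the plan says.** **Notification.** Section 10.2.4.3 defines the reportable period as running from consent "up to 2 months after the withdrawal of Regorafenib, and 3 months after the withdrawal of Irinotecan for female patients", and it applies the same limits to female partners of male patients. The next sentence adds: "Every pregnancy or suspicion of pregnancy should be notified to the Sponsor without any further delay".

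**Contraception.** Criterion 12, in the synopsis and in section 4.2, requires women and men to use contraception "until at least respectively 7 months and 4 months after the last study drug administration of Regorafenib". For the second drug of the combination, the same criterion sets the periods as "respectively 6 months and 3 months after the last study drug administration of Irinotecan". Section 10.2.3 repeats these periods. For regorafenib they are "respectively 7 months and 4 months in men sexually active with women of childbearing potential after last dose of regorafenib", the first figure being for women. For the other drug it says: "For Irinotecan, the durations of contraceptives for women of childbearing potential (WOCBP) and men are respectively 6 months and 3 months".

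**Related clauses.**
- Section 10.2.3 also states: "The pregnancy should be followed up to determine outcome". It gives no time limit.
- Section 10.2.4.3 sends serious pregnancy outcomes to the SAE route.
- Section 10.2.4.1 keeps that route open after 30 days for related events only: "Every SAE occurring beyond the 30 days period after the withdrawal of the investigational product, judged by the investigator to be related".
- Section 8.1 calls pregnancy a serious adverse event, in its list of reasons for stopping treatment.
- The chart in section 10.2.4.4 says notification starts when the pregnancy is confirmed and gives no end date.

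**The concern.** The contraception period is the protocol's own statement of how long after the last dose a pregnancy should be avoided, and section 10.2.3 bases it on potential genotoxicity and teratogenicity. One would expect a pregnancy within that period to be notifiable. As section 10.2.4.3 is written, a site could properly conclude that a pregnancy arising late in the period need not be notified.

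Scheduled assessments do not fill the gap. Sections 5.1 to 5.3 place the pregnancy test at screening and on day 1 of each cycle. It is not listed at the end-of-treatment visit (5.4). The last adverse-event contact is at 30 days, and the later every-other-month contacts record only vital status and anti-cancer medication (5.5). After treatment, detection relies largely on sites knowing their reporting duty.

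What is at stake is the completeness of safety information on exposed pregnancies. The efficacy analysis, the event count and the power are not involved.

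**Working it through.** **Inputs, in months after the last dose**

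| | Contraception (synopsis, 4.2, 10.2.3) | Notification (10.2.4.3) |
|---|---|---|
| Regorafenib, women | 7 | 2 |
| Regorafenib, men / partners | 4 | 2 |
| Irinotecan, women | 6 | 3 |
| Irinotecan, men / partners | 3 | 3 |

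The three places that give contraception periods agree with one another.

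**Shortfall by drug** (contraception minus notification; share covered = notification / contraception)

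- Regorafenib, women: 7 − 2 = 5 months; covered 2/7 = 29%.
- Regorafenib, partners: 4 − 2 = 2 months; covered 2/4 = 50%.
- Irinotecan, women: 6 − 3 = 3 months; covered 3/6 = 50%.
- Irinotecan, partners: 3 − 3 = 0 months; covered 3/3 = 100%.

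**By arm** (78/2 = 39 planned patients each)

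Arm B receives regorafenib only, so the gaps are 5 and 2 months.

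Arm A receives both drugs. Two assumptions are needed that the protocol does not state: withdrawal means the last dose, and the later of the two limits governs. Let d be the number of months by which irinotecan stops after regorafenib (negative if it stops first), with time counted from the last regorafenib dose. Then:

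- Notification ends at max(2, d + 3).
- Contraception ends at max(7, d + 6) for women and max(4, d + 3) for men.

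| Order of stopping | Notification ends | Gap, women | Gap, partners |
|---|---|---|---|
| d ≤ −1 | 2 | 7 − 2 = 5 | 4 − 2 = 2 |
| Full last cycle (irinotecan day 15, regorafenib day 22): d = −7 days ≈ −0.23 | 2.77 | 7 − 2.77 = 4.23 | 4 − 2.77 = 1.23 |
| d = 0 | 3 | 7 − 3 = 4 | 4 − 3 = 1 |
| d ≥ 1 | d + 3 | (d + 6) − (d + 3) = 3 | (d + 3) − (d + 3) = 0 |

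The range is 3 to 5 months for women and 0 to 2 for partners. For women the gap never closes. For partners it closes only if irinotecan stops at least one month after regorafenib.

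**Does another clause extend the window?**

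- The second sentence of 10.2.4.3 can be read as restating the duty within the period just defined, or as open-ended. On the open-ended reading the limits in the preceding sentence have no function, so the text needs editing either way.
- The chart in 10.2.4.4 fixes when notification starts and does not say when the duty ends.
- Sections 8.1 and 10.2.4.1 together give a 30-day route that afterwards covers only events judged related. This is shorter than the pregnancy window and uses a different form.
- Follow-up to outcome (10.2.3) presupposes a known pregnancy, and it comes after text about pregnancy during treatment.
- Sending serious outcomes to the SAE route covers the outcome and not notification of the pregnancy itself.

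**The case against.** Contraception length and the immediate-notification window are separate parameters, and no clause says they must be equal. The requirement to notify every pregnancy, read with the chart in 10.2.4.4, supports a general duty without an end date. Related serious outcomes remain reportable at any time. The notification form and its filling guide (Appendix 11) are not in the supplied text and might clarify the period. The population has refractory metastatic disease with an assumed control median survival of 7 months from randomisation (9.1), so many patients will not live through the months in question. The arm A decimals rest on conventions the protocol does not state.

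Much of this limits the size of the problem without removing it. Few cases are expected, and the number of patients of childbearing potential is not given. For arm A, the range is what should be relied on; the full-cycle figures are an illustration. Appendix 11 remains unchecked. But the protocol states specific limits, offers no reason for them to be shorter than its exposure-risk period, and contains no clause that clearly overrides them. A reading that saves the text only by making its stated limits redundant is itself a reason to correct it.

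**Conclusion.** The point holds. The stated window is short by 5, 2 and 3 months in three of the four drug-by-sex combinations and equal in the fourth. In arm A the gap is 3 to 5 months for women and 0 to 2 for partners, given the two assumptions above. Confidence in the mismatch is high. Its practical effect is small: contraception is an eligibility condition, 78 patients are randomised, and efficacy and power are untouched. The sponsor should correct it as a safety-reporting inconsistency; it does not threaten the trial's conclusions.

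A likely explanation, which is inference only, is an update that was not carried through. Section 10.2.3 bases its regorafenib durations on a recommendation dated September 2020, whereas first inclusion was September 2019.

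**What to change.** Reconcile 10.2.4.3 with criterion 12 (synopsis and 4.2) and with 10.2.3:

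- Let the notification window last at least as long as whatever contraception period the protocol keeps for each drug and sex, with the later limit applying when both drugs were given.
- Make the following sentence refer to that same window.
- Check Appendix 11 against the result.

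Useful additions beyond the core edit:

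- a pregnancy question at the existing every-other-month contacts (5.5);
- one consistent reporting route in 8.1 and 10.2.4.3;
- a statement on notification after study end. Inclusion is planned to close in January 2025 and the study to end in June 2025, so under the current 7-month contraception period a window of equal length could outlast the study for women enrolled late.

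The core change edits two adjoining sentences and uses an existing form. If the current contraception periods are kept, it adds up to 5 months of notification duty per woman and up to 2 months per male patient's partner after regorafenib. The sponsor would also have to decide whether the change counts as substantial under section 12.6.
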